#### 6.3.1 Additional Safeguards:

- Non-English speakers: Excluding this group would compromise the principle of justice in clinical research. For groups likely to be enrolled given our known demographics (for example, Spanish-speaking and Somali-speaking), we will translate informed consent forms (ICF) and use professional interpreters during both the consent and follow-up periods. These interpreters are available to our group during daytime hours by telephone. We will request the use of the Short Form Consent for non-English speaking participants, and adhere to the regulations surrounding its use. When the translated ICFs become available, they will be used for non-English speakers. We will make every effort to have Spanish-speaking research coordinators on our team and access to interpreter services.
- *Employees or students of the researcher:* This group will be excluded.
- *Undervalued or disenfranchised social group:* We will assure confidentiality, that they have the right to withdraw at any time without penalty, and they have the freedom to refuse to answer questions.
- Active members of the military (service members), DoD personnel (including civilian *employees*): The status of participants of this group is not asked during the study nor known by study staff, and therefore vulnerability is not increased for anyone in this group.
- Individual or group that is disadvantaged in the distribution of social goods and services such as income, housing, or healthcare: We will assure that information from participants in this study will be treated with the strictest confidentiality, that participants have the right to withdraw at any time without penalty, and they have the freedom to refuse to answer questions. When needed, every effort at making accommodations will be made for those who do not have a home address, such as medication pick-up space in a local shelter or emergency department. If the potential participant needs a phone in order to comply with study needs, one will be provided for the duration of the individual's enrollment.
- Individual or group with a serious health condition for which there are no satisfactory standard treatments: We will assure confidentiality, that they have the right to withdraw at any time without penalty, and they have the freedom to refuse to answer questions. We will also employ the teach-back method to ensure participants understand risks and demands of study participation.
- Individual or group with a fear of negative consequences for not participating in the research (e.g. institutionalization, deportation, disclosure of stigmatizing behavior): The status of participants from these groups is not asked during the study nor known by study staff, and that vulnerability is not increased for anyone in this group.

#### 6.4 Number of Participants

Enrollment will occur remotely via the previously described methods for interested participants presenting to one of the PCR-testing sites or via self-referral to the study. Patients in assisted

living facilities do qualify for this study. The total number at each site will be affected by local incidence rates at the time of enrollment. We anticipate that at least 100 participants will be enrolled at each participating institution.

## 7.0 Sharing of Results with Participants

7.1 Sharing of results:

Data collected within this study will be obtained from the participants themselves or will be obtained from the electronic medical record and thus are already available to the patient and treatment team. Any testing of biospecimens will occur at a later time point and do not have specific clinical relevance. Research results will be shared with the participant and/or the participant's primary care provider when determined by the research clinician to be clinically relevant.

7.2 Sharing of genetic testing

Not applicable. No genetic testing will be conducted

## 8.0 Withdrawal of Participants

8.1 Withdrawal Circumstances:

Participants may withdraw from the study at any time for any reason. Participants may be withdrawn from the study without their consent if at any point they develop an exclusion criteria that makes it unsafe for them to continue in the study. All data from patients withdrawn from the study will be analyzed up until time of withdraw. Clinical progression after withdrawal may be assessed via EHR or vital status review or by reaching out to patients or their contacts.

8.2 Withdrawal Procedures:

If patients choose to withdraw, study procedures including intervention and follow-ups will stop. Given the remote nature of this study, written notification is not required. If the patient chooses to withdraw, the study team will ask if the patient is willing to allow continued electronic medical record evaluation for the determination of study endpoints (partial withdrawal). We will also ask if the patient wishes to withdraw consent for the use of future biologic specimens. If the patient declines to participate in any component of research, no further study data will be collected, biologic samples will be destroyed, but existing study data may be used. Each of these circumstances will be documented and stored as a study document.

8.3 Termination Procedures:

Upon trial termination, study outcomes will be followed until completion. Case report forms and collection templates will be maintained in paper format (when applicable) and electronically for 7 years in accordance with regulations. Collected data will be used for secondary analyses with approval of the principal investigators in a deidentified fashion. Data entry will be completed, checked for accuracy, and locked for analysis within 1 year of enrollment of the final patient.

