#### 4.5 Dose Modification:

Participants will be advised to take ivermectin and its matching placebo on an empty stomach with water. Ivermectin and its matching placebo are provided in asmall blister-packed square.

Participants will be advised to take all other medications (i.e., metformin and/or fluvoxamine and their matching placebos) with a small amount of food (not on an empty stomach).

With mild side effects, participants will be reminded to take the tablets at the end of a meal, as opposed to the beginning of or "with" a meal. They will also be advised to stay upright for about an hour after consuming the study tablet.

With mild-moderate side effects, if the patients find them tolerable, patients will be advised the above, and that side effects should decrease after about 5 days of the medication. With moderate or moderate-substantial side effects that the patient finds intolerable, participants will be advised that they can break tablets in half if they feel they are having a non-tolerable medication side effect. Each type of active drug and placebo pill in this study can be broken in half. Dose modification will be recorded in the study database.

In the event of substantial side effects, participants may discontinue the study medication and stay in the study to complete follow up. This treatment discontinuation (whether in the placebo or any active treatment group), will not be considered study withdrawal.

4.6 Placebo:

The placebo will be tablet of microcrystalline cellulose, made to exactly mimic metformin or fluvoxamine or ivermectin.

4.7 Study Drug Handling:

Fairview IDS, part of M Health Fairview, will oversee the study and provision of bulk and prepackaged study drug (including placebo) to participating sites. Participants will be given a study number coded by site (e.g. 01-001, 02-001, etc.). The pharmacy team involved will be unblinded to patient randomization. All other members of the clinical care team and the participants will be blinded to treatment allocation. The research team statisticians will remain blinded (additional information in Section 13, Statistical Considerations).

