#### 5.4.3 Lab Collection:

Labs will be considered optional if patients want to participate but not collect the nasal swab and/or stool. For interested and willing patients, labs will be done on approximately Day 1, 5, and 10.

The SARS-CoV-2 PCR may be assessed via self-collect anterior nasal swab, which may be done over phone or video with the RC if the patient prefers this aid. Detailed instructions for the patient are in Appendix B, the patient manual.\*

The GFR blood tests may be collected by the clinic, mobile phlebotomy, or finger-prick, with the option of it being done while on secure video or phone with the RC if the patient prefers this aid. Blood will be collected in a microtainer tube and placed in approved shipping materials that will then be returned to the lab via courier or mail.

Stool sample collection is optional and would be done with a self-collect microbiome kit. Patients will be given detailed lab collection procedures for each test.

Missing biospecimens will not constitute protocol deviations.

5.4.4 Seeking Medical Care:

Patients will be advised to seek medical care, as they would if they were not in the study, including other treatments of Covid-19. Participants will be advised that the distribution of home oxygen monitors is not meant to prevent them from seeking medical care, and that they should seek medical care as they would whether they were in the study or not.

5.5 Follow-up Procedures:

CONFIDENTIAL

Data on clinical progression may be collected on any consented patient by EHR review, from contact if patient not available, by patient self-report (phone, survey, email, text), or by vital records search.

RC's may contact patients on Day 2 to assess side effects or questions. If patients experience side effects that they find distressing, the RC's will discuss approaches to minimize side effects (See Section 4.6 Dose Modification), and to advise the patients that side effects usually subside after about 5 days.

Participants will be asked to track symptoms (including temperature and oxygen saturation), and medication adherence daily. Patients will receive a thermometer and oxygen saturation monitor with their study drug (details below). Study personnel will attempt to contact with patients about every 2 to 3 days during the 14-day intervention window to review study drug adherence, and review symptoms for possible adverse events.

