Patients will be followed for 28 days for disease severity. Follow-up contact with patient or family and electronic medical record review will determine the primary and secondary efficacy endpoints.

A patient who has a visit to an emergency department for COVID-19 related symptoms, (determined by current CDC definition of COVID-19 related symptoms or treating team), or hypoxia (two measurements of O2 saturation  $\leq 93\%$  or supplemental oxygen required to maintain saturation  $\geq 93\%$ ) will have achieved a positive result for the primary outcome.

Patients who experience a primary outcome before enrollment (i.e. ED visit at which they received their +SARS-CoV-2 result) will be followed for occurrence of a primary or secondary outcome after T0 (Day 1 in the study).

- Patients who are hospitalized will stop the study drugs.
- Secondary outcomes will be assessed at 14 and 28 days, including in patients who drop out of doing the study tasks. EHR search of outcomes will be assessed of all patients who enroll.
- Patients in the treatment arm who visit an urgent care or emergency department and are sent home without being admitted should continue the study drug through day 14, unless otherwise directed by the treating physician in the emergency department or urgent care.
- Long-Covid symptoms will be assessed at approximately 1-month intervals after the completion of the 14-day study treatment period.

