## 6.0 Study Population

6.1 Study Population:

Adults age 30-85 years with no prior history of SARS-CoV-2 infection and with BMI in overweight or obesity category. We will not exclude patients who have diabetes, but we will exclude patients on insulin or a sulfonylurea. Symptoms are not a requirement to enroll in the because of their subjective nature and because of wanting to start patients on study drug early in the disease course.

6.2 Inclusion and Exclusion Criteria:

Inclusion criteria	Exclusion criteria
- Positive laboratory test for active SARS-CoV-2	- Hospitalized, for COVID-19 or other reasons.
viral infection based on local laboratory standard	- Symptom onset greater than 7 days before
(i.e. +PCR) within 3 days of randomization.	randomization (symptoms not required for inclusion).
- no known history of confirmed SARS-CoV-2	- immune compromised state (solid organ transplant,
infection	bone marrow transplant, AIDS, on chronic high dose
- Age $\geq$ 30 years and $<$ 85 years	steroids)
- BMI $\geq 25$ kg/m  by self-report height/weight or	- Hepatic impairment (Child-Pugh B and C) or
$>= 23 \text{kg/m}^2$ in patients who self-identify in	that in the opinion of the investigator, would affect safety
Asian or Latinx background. 	- Inability to obtain informed consent
- Has an address and electronic device for	- Enrollment in another blinded RCT for COVID-19
communication	- Already received an effective (FDA approved/EUA*)
- GFR>45ml/min within 2 weeks for patients	therapy for COVID-19 (currently monoclonal antibody
>75 years old, or with history of heart, kidney, or	treatment)
liver failure.	- Alcohol use disorder

- Other unstable medical condition or combination of home medications that in the view of the PI make it unsafe for the individual to participate

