Secondary outcomes will be analyzed using generalized linear models with an appropriate distributional assumption and/or normalizing transformations. These analyses will adjust for study site and other prognostic information as appropriate. Time-to-event outcomes will be compared using Kaplan-Meier and log-rank tests as well as Cox proportional hazards models that adjust for prognostic variables. Ordinal endpoints will be analyzed using proportional odds regression models that adjust for prognostic variables and supplemented by logistic regression models for each ordinal threshold. These analyses will be supplemented by descriptive cumulative statistics for each ordinal category by treatment group. Detailed plans for primary, secondary and supplemental analyses will be provided in the SAP prior to conducting any unblinded data analyses.

All analyses will be carried out using R version 3.6.1 or newer.

12.3 Data Integrity:

The principal investigator will manage oversight of quality control for collected data. Recruitment of subjects will be performed using inclusion/exclusion criteria defined above Study data will be recorded within a REDCap database, which is HIPAA complaint, password protected with variable assignable security access and an audit trail consistent with all regulatory requirements for maintenance of clinical trial data. Data summaries and quality control checks will be run routinely.

12.4 Missing Data:

Research coordinators will make a consistent effort to ascertain all study data within the protocol specified windows, as well as outside these windows as needed. Participants who fail to respond will be contacted by study staff multiple times, and family will be contacted as well, prior to being recorded as lost to follow up. All data collected on a participant prior to loss to follow up or withdrawal of consent will be included in analyses. Missing values will be multiply imputed using chained equations and predictive mean matching via the mice package and the effect estimate and confidence intervals will reflect the uncertainty in these missing values. For the primary outcome variables, sensitivity analyses that are biased towards the null will be carried out by assuming missing outcomes in the placebo arm follow the estimated distribution in the treatment arm, and vice versa for missing outcomes in the treatment arm. Additional details will be provided in the SAP.

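### Section 8.1 allows withdrawal from the study, not only from study drug, for a new exclusion criterion, cuts the analysis at that point and makes later outcome capture optional, in conflict with sections 4.5, 5.5 and 5.5.2

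*Protocol*

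**What the plan says.** **Section 8.1, Withdrawal Circumstances.** The trigger is a health or safety change after randomisation, and the decision is not the participant's: "Participants may be withdrawn from the study without their consent if at any point they develop an exclusion criteria that makes it unsafe". The analysis rule follows: "All data from patients withdrawn from the study will be analyzed up until time of withdraw". The next sentence allows, but does not require, later ascertainment: "Clinical progression after withdrawal may be assessed via EHR or vital status review or by reaching out to patients or their contacts".

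**Section 4.5, Dose Modification.** When study drug is stopped for substantial side effects, the participant stays in follow-up: "This treatment discontinuation (whether in the placebo or any active treatment group), will not be considered study withdrawal".

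**Section 5.5, Follow-up Procedures.** Hospitalised patients stop study drug. Secondary outcomes at Days 14 and 28 are also sought in people who no longer do the study tasks, and "EHR search of outcomes will be assessed of all patients who enroll". The opening of 5.5 is permissive: "Data on clinical progression may be collected on any consented patient by EHR review". The Day 28 entry in 5.5.2 adds a vital status search for everyone randomised.

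**Section 6.2.** The exclusion list includes "Hospitalized, for COVID-19 or other reasons", other unstable medical conditions and a list of excluded drugs.

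**Section 12.4, Missing Data** (the second section with that number). "All data collected on a participant prior to loss to follow up or withdrawal of consent will be included in analyses". Missing values are multiply imputed. A sensitivity analysis for the primary outcome gives missing outcomes in each arm the distribution estimated in the other arm.

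**The concern.** Safety can be a reason to stop study drug. It is not a reason to stop telephone contacts, symptom and oximetry logs, or record review, none of which exposes the participant to drug. Section 8.1 joins the two and then fixes an analysis cut-off at the moment of withdrawal.

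The missing outcomes would be created by a staff decision, and the reason for that decision is a change in health or treatment that may be related to the endpoint and may differ by arm. The modified intention-to-treat definition in section 12 removes only screen failures and people who took no study drug, so someone withdrawn under 8.1 stays in the analysis set with a truncated record. If no event has occurred by then, the 14-day status is undetermined. The protocol does not say whether an event found later by record search counts, or whether the outcome is imputed.

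**Working it through.** **1. Which triggers can cost a primary event.** The primary endpoint (3.1) is an emergency department visit for COVID-19 symptoms, including hospitalisation or death, or a fall in oxygen saturation, by 14 days.

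- COVID-19 hospitalisation: listed in 6.2, but it is already an event, and 5.5 stops drug only. No primary event is lost.
- Emergency department visit or low saturation: neither is an exclusion criterion, so neither triggers 8.1.
- Fall in GFR: largely moot. Section 9.0 plans no safety laboratory tests after the start, and a pending GFR that returns below 45 ml/min is a screen failure under 5.3.1.
- New unstable condition, hospitalisation for another reason, or starting an excluded drug: these can arise before Day 14 in someone without an event. They are the triggers that matter.

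**2. What the planned searches recover.** A record search can find emergency visits and admissions, and a vital status search finds deaths. Home oximetry is logged by the participant (5.5, 5.5.1), so once contact ends a low reading would usually appear in neither source. The monthly long-COVID questionnaire has no record-based substitute either. The partial-withdrawal question in 8.2 is put only to participants who choose to leave, so withdrawal by staff has no stated follow-up procedure.

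**3. Size, as illustration only.** The protocol has no figure to reproduce here. From 12.3.1: 20% on control and 11% on drug, so the relative reduction is 1 − 11/20 = 45%. Assumed, with no source in the protocol: a share w of each arm is withdrawn under 8.1, 40% of them would have an event, and no later event is counted. The true rate is then (1 − w) × base + w × 40%.

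- w = 5% drug, 2% control: 0.95 × 11 + 0.05 × 40 = 12.45%; 0.98 × 20 + 0.02 × 40 = 20.4%; reduction 39.0%.
- w = 3% and 1%: 11.87% and 20.2%; reduction 41.2%.
- w = 5% and 5%: 12.45% and 21.0%; reduction 40.7%.
- w = 2% and 5%: 0.98 × 11 + 0.02 × 40 = 11.58%, and 21.0%; reduction 44.9%.
- w = 1% and 5%: 0.99 × 11 + 0.01 × 40 = 11.29%, and 21.0%; reduction 46.2%.

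An analysis that gives those withdrawn the completers' average risk shows 45% every time. It overstates the effect in the first three cases, is almost right in the fourth and understates it in the fifth.

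**4. What the planned sensitivity analysis recovers.** In the 5% and 2% case, swapping the arm distributions gives 0.95 × 11 + 0.05 × 20 = 11.45% and 0.98 × 20 + 0.02 × 11 = 19.82%, a reduction of 42.2%. That is about half the distance from 45% to 39.0%.

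**The case against.** A reader might infer from 8.1 that primary outcomes are lost in the participants who worsen. The documents do not support that. Worsening as such does not trigger withdrawal: two endpoint components are not exclusion criteria, and the third counts before any withdrawal could follow.

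Nor does section 12.4 bar later events. It says which data are included, it concerns loss to follow-up and withdrawn consent, and it does not mention withdrawal by staff. Read generously, 8.1, 5.5 and 5.5.2 together mean that study tasks stop while outcomes are still sought. Chained-equation imputation can condition on participant data, so those withdrawn need not receive average risk, and the swap analysis leans towards the null. The illustration uses single-cell rates and invented withdrawal shares. Details of analysis may also sit in the SAP, which is not at hand.

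Most of this stands, and it limits the point to outcomes that can be lost. It does not remove the point. The cut-off in 8.1 is a stated rule, not a detail left open, and it conflicts with the generous reading. The vital status search covers deaths only, and the statements on collecting progression data in 8.1 and at the start of 5.5 are permissive. The swap analysis uses the other arm's rate, not the risk of people withdrawn for a health reason. Single-cell rates do not exaggerate the illustration: the marginal metformin rates from the 12.3 table, (11 + 6 + 6)/3 = 7.67% against (20 + 11 + 11)/3 = 14.0%, give 9.28% and 14.52% in the 5% and 2% case, a reduction of 36.1% against 45.2% in completers.

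**Conclusion.** The point holds as an inconsistency that should be corrected. Section 8.1 permits withdrawal from the study on a health trigger, states an analysis cut-off and leaves later ascertainment optional, while 4.5, 5.5 and 5.5.2 point the other way. Primary outcomes can be lost or left out after a new unstable condition, a non-COVID hospitalisation or the start of an excluded drug, with home oxygen-saturation events the most exposed.

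The size and direction of any bias cannot be stated. The protocol gives no expected number of such withdrawals, no split by arm and no event risk for them. The range from 39.0% to 46.2% against an apparent 45% rests wholly on assumed inputs and on no later event being counted. The record and vital status searches would narrow the gap, and the planned sensitivity analysis offsets it only in part.

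**What to change.** Reconcile 8.1 with 4.5, 5.5 and 5.5.2 in three statements:

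1. A stop initiated by the investigator because an exclusion criterion has developed ends study drug only. The decision on study drug stays with the existing clinical rules.
2. Outcome follow-up to Day 14 and Day 28, and the monthly contacts, continue unless the participant withdraws consent.
3. All outcome data obtained with permission after the stop are analysed in the randomised arm. This replaces the cut-off sentence in 8.1. A matching sentence in 12.4 Missing Data would remove doubt about events found later.

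The cost is protocol wording. The contacts, the record search and the vital status search are already planned.

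Withdrawal of consent keeps its present handling under 8.2.
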